11.3 Analysis Plans

Patients' demographic information at baseline will be collected. We will use mean, standard deviation, median, and range to summarize continuous variables such as blood pressure, heart rate, temperature, pain medication usage, pain and nausea scores, and frequency counts and percentages for categorical variables such as adverse events. We will use the student t-test or the Wilcoxon rank sum test to compare continuous variables between two patient groups. The Fisher's exact test or Chi-square test will be applied to assess the association between two categorical variables. Linear regression will be utilized to assess the effects of patient prognostic factors on the post-operative pain medication usage and the pain score in the first 24 hours.

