5.0 Treatment Plan

5.1 Preoperative

- 5.1.1 After consents for surgery and study participation are signed, patients will be registered for the trial by the research staff. Patients will be randomized (1:1) using a computerized randomization scheme.
- 5.1.2 Patients will be randomized (1:1) to one of two groups:
 - Group I, Treatment Group: Patients receive a caudal nerve block prior to surgery and receive general anesthesia during surgery.
 - Group II, Control Group: Patients receive general anesthesia during surgery without a caudal nerve block.
- 5.1.3 Patients in both groups will receive Famotidine 20mg IV, up to 1-2mg IV Midazolam and 25-50mcg IV Fentanyl in the holding area prior to the start of surgery.
- 5.1.4 Patients who are age 70 and older will not receive Midazolam 2mg IV in the holding area prior to the start of surgery.
- 5.1.5 Patients in Group II will receive Fentanyl 50-250mcg IV in the holding area prior to the start of surgery.

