6.0 Pretreatment Evaluation

A complete history including age, history of use of chronic pain medication, history of anticoagulants and history of allergies to local anesthetics will be obtained within 4 weeks of randomization.

Physical examination including height, weight and body mass index will be recorded within 4 weeks of surgery.

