11.0 Statistical Consideration/Number of Patients

11.1 Objectives

This is a trial to determine whether the use of a caudal nerve block (CNB) and general anesthesia in patients undergoing surgery for penile prosthesis results in decreased post-operative pain compared with patients having only general anesthesia. Patients will be randomized with a 1:1 ratio to receive either CNB or general anesthesia. The primary endpoint is the post-operative pain medication usage during PACU stay. The secondary endpoint is the proportion of patients with no pain immediately after surgery.

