11.2 Sample Size and Power

This is a randomized, blinded trial designed to evaluate the efficacy of the caudal nerve block (CNB) in combination with the general anesthesia (GA) comparing to the GA-only on patients undergoing penile prosthesis surgery. The primary objective is to determine if the CNB + GA can result in decreased post-operative pain medication usage during PACU stay comparing to the GA-only. One hundred four patients will be randomized with a 1:1 ratio to each of the treatment arms. In a retrospective trial. PA15-0080, the mean ± SD for the post-operative pain medication usage was 21.6 \pm 13.6 mg for the GA-only group (n=59) and 13.9 \pm 11.0 for the CNB + GA group (n=26). With a sample size of 104 patients (52 for each treatment arm), the study will have at least 81% power to detect the difference in post-operative pain medication usage between 21.6 for the GA-only arm and 13.9 for the CNB + GA arm assuming a common standard deviation of 13.6 as observed in the retrospective study. A twosided Type I error rate of 0.05 was used (EAST 6.3.1, Cytel Inc 2015). One interim analysis will be performed to allow for the early termination of the trial in light of evidence that the CNB + GA treatment is superior to the GA-only treatment or there is no difference between the two treatment arms. In order to provide an overall significance level of 0.05 for the study, the interim analysis will use an O'Brien-Fleming stopping rule. The interim analysis will be performed when 52 out of the 104 patients have been observed. Using O'Brien-Fleming test boundaries, we will reject the null hypothesis at the interim and final analyses when the absolute value of the Z-score is larger than or equal to 2.963 and 1.969 (the corresponding p-values are ≤ 0.003 and 0.049), respectively. We will reject the alternative hypothesis at the interim and final analyses when the absolute value of the Z-score is less than or equal to 0.338 and 1.969 (the corresponding p-values are ≥ 0.736 and 0.049), respectively. The secondary objective is to compare the post-operative pain in the first 24

hours after surgery between the two treatment arms. The patients will be blinded for the treatment assignment to avoid potential biases.

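### The arm comparison is unadjusted and no adjusted arm effect is specified, although age and BMI are recorded before surgery and a regression on medication usage is already planned

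*Combined protocol and SAP*

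**What the plan says.** Section 11.1 defines the endpoint: "The primary endpoint is the post-operative pain medication usage during PACU stay". For comparing continuous variables between the two groups, section 11.3 offers a t-test or a Wilcoxon rank sum test, neither with covariates. A separate sentence says "Linear regression will be utilized to assess the effects of patient prognostic factors on the post-operative pain medication usage", and continues to the pain score in the first 24 hours. The prognostic factors are not named. Arm is neither listed as a term nor ruled out, and no adjusted arm effect is mentioned.

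Section 6.0 has age taken in the history within 4 weeks of randomization, and adds: "Physical examination including height, weight and body mass index will be recorded within 4 weeks of surgery". Section 5.1 describes 1:1 computerized randomization and states no stratification factor. Section 11.2 bases power on the unadjusted standard deviation.

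**The concern.** When a baseline variable predicts the outcome, including it in the model for the arm effect lowers the residual variance and removes the part of any chance imbalance that it explains. Here the covariates are collected anyway and a regression on medication usage is already planned, yet nothing commits the trial to estimating the arm effect from such a model. No stratification factor is stated that would balance age or BMI by design. Age also enters the care pathway (section 5.1: "Patients who are age 70 and older will not receive Midazolam 2mg IV"), although that rule covers both arms and the documents do not link it to opioid use after surgery.

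At stake is a modest amount of precision, plus clarity. With the factors and role of the regression left open, an adjusted arm effect could later be fitted with covariates chosen after the data are seen.

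**Working it through.** **Inputs from section 11.2.** Two-sided alpha 0.05 ("A twosided Type I error rate of 0.05 was used"). Difference 21.6 − 13.9 = 7.7 mg ("between 21.6 for the GA-only arm and 13.9 for the CNB + GA arm"). SD 13.6 mg ("assuming a common standard deviation of 13.6 as observed in the retrospective study"). 52 per arm, with one interim at 52 of 104 patients. Efficacy bounds |Z| ≥ 2.963 and 1.969; interim futility bound |Z| ≤ 0.338.

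**Step 1: reproduce the plan's power.**
- SE of the difference = 13.6 × √(2/52) = 2.667 mg.
- Drift = 7.7 / 2.667 = 2.887.
- Fixed design, normal approximation: 82.3%.
- Two looks at information fraction 0.5 with the stated bounds, by numerical integration: 0.8125. A simulation of 4 million trials gives 0.8128.
- Two-sided type I error in that simulation: 0.0485 with futility binding, 0.0501 with futility ignored.

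The plan's statement that "the study will have at least 81% power to detect the difference in post-operative pain medication usage" is therefore confirmed for the unadjusted test.

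**Step 2: add age and BMI.** Let R² be the share of within-arm variance in usage that the two covariates explain. The documents give no value, so a range is assumed.
- Drift without covariate cost = 2.887 / √(1 − R²).
- Estimating two covariate slopes inflates the variance by about 1 + 2/(104 − 4 − 1) = 1 + 2/99 = 1.0202.
- Drift with cost = 2.887 / √[(1 − R²) × 1.0202].

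| Assumed R² | Power, cost ignored | Power, cost included |
|---|---|---|
| 0 | 0.8125 | 0.8048 |
| 0.02 | 0.8201 | 0.8125 |
| 0.05 | 0.8317 | 0.8243 |
| 0.10 | 0.8510 | 0.8440 |
| 0.20 | 0.8892 | 0.8831 |

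Break-even is where (1 − R²) × 1.0202 = 1, so R² = 0.0198, or about 0.02. At R² = 0 the loss is 0.8125 − 0.8048 = 0.0077, or 0.8 points. The cost factor is an approximation applied at both looks. At the interim it would be nearer 1 + 2/(52 − 4 − 1) = 1.043; using that value lowers each costed figure by about 0.1 point, and the loss at R² = 0 stays under one point.

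**Step 3: what a chance imbalance could do.** If R² were 0.10, an imbalance 1.96 standard errors from zero would move the unadjusted estimate by 1.96 × 2.667 × √0.10 = 1.7 mg at the final look. At the interim, with 26 per arm, SE = 13.6 × √(2/26) = 3.77 mg and the shift is 1.96 × 3.77 × √0.10 = 2.3 mg. The target difference is 7.7 mg. These shifts are part of the ordinary sampling error that the unadjusted test already allows for.

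**The case against.** The strongest reply is that nothing is broken. A randomized, unadjusted comparison is valid, its type I error already covers chance imbalance, and the stated power reproduces. The planning SD is also cautious. With the two SDs reported in section 11.2, the root-mean-square is √[(13.6² + 11.0²)/2] = 12.37 mg, and the same boundaries give about 88% power without covariates. All of this stands.

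The benefit is also unproven. PACU fentanyl in section 5.3 follows the pain score and not weight. Section 4.2 excludes BMI above 40, chronic pain medication and chronic pain syndromes, which may narrow what baseline factors can explain. R² could be near zero. That stands too, and is why the range starts at 0.

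A linear model may fit poorly. Usage cannot be negative, pain scores of 0 to 2 receive no treatment, and the SDs are 63% and 79% of the means (13.6/21.6 and 11.0/13.9), so skew and zeros are plausible. Robust standard errors and a retained rank test as sensitivity analysis answer this in large part.

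A reader might go further and infer that the regression leaves arm out, that it concerns exactly the primary endpoint, or that precision is certainly being thrown away. The documents support none of these. The model terms are unlisted, so the text is silent on arm. The words about the first 24 hours may qualify usage as well as the pain score, whereas the primary endpoint is PACU usage. Any loss of precision depends on an R² that is not given.

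**Conclusion.** The point holds as an inexpensive improvement to a valid analysis. Section 11.3 specifies no adjusted arm effect, although suitable baseline covariates are recorded before surgery. Relative to 81.2% unadjusted, and after the cost of two covariates, adjustment changes power by about −0.8 points at R² = 0, nothing at 0.02, +1.2 at 0.05, +3.2 at 0.10 and +7.1 at 0.20. These figures assume a 7.7 mg difference, an SD of 13.6 mg, the stated boundaries and the approximate cost factor. The R² values are assumptions.

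It would be wrong to conclude that the trial is underpowered or that its primary result would be biased. The case for changing rests on an uneven trade: under one point at risk, several points available if age and BMI are moderately prognostic, and an arm model fixed before unblinding.

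**What to change.** In section 11.3, name one primary analysis for PACU pain medication usage: a linear regression on arm, age and BMI with robust standard errors. Test the arm coefficient against 2.963 and 0.338 at the interim and 1.969 at the final look. Report the unadjusted t-test or Wilcoxon test as a sensitivity analysis. Say whether the existing prognostic-factor regression is this model or a separate exploratory one, and whether its usage outcome covers the PACU stay or 24 hours.

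The cost is a wording change made before the interim data are seen. It needs no new data and no change to sample size or boundaries. The statistical price is the possible loss of under one point of power if the covariates explain almost nothing. The rank test would no longer be an option for the primary result.

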12.0 Reporting Requirements

Please see Appendix A: Guidelines for AE Reporting

13.0 Data Safety Monitoring Board

During the protocol review and approval process, The University of Texas M.D. Anderson Cancer Center IRB (Institutional Review Board) determines the level of safety monitoring required for each protocol on a case-by-case basis.

The principal investigator is responsible for submitting adverse events (AEs) to The University of Texas M.D. Anderson Cancer Center IRB.

All protocol participants must be registered in The University of Texas M.D. Anderson Cancer Center PDMS (Protocol Data Management System).

